Visit Information	Visit 1 Screening, Baseline, Treatment 1 Fitting	Visit 2 Treatment 1 Follow-up 1 Optimization	Visit 3 Treatment 1 Follow-up 2	Visit 4 Baseline Treatment 2 Fitting	Visit 5 Treatment 2 Follow-up 1 Optimization	Visit 6 Treatment 2 Follow-up 2
Time Point	Day 0	Day 3±1 from V1	Day 12±2 from V2	Day 7±3 from V3 Fitting Day 0	Day 3±1 from V4	Day 12±2 from V5
Estimated Visit Duration	2.5 hours	1.0 hours	1.5 hours	2.5 hours	1.0 hours	1.5 hours
Baseline Inclusion/Exclusion Criteria	x					
Continuance				x		
Lens Selection	x	x (if modified)		x	x (if modified)	
Lens Insertion	x	x	x	x	x	x
10 Minute Settling	x	x (if modified)		x	x (if modified)	
Visual Satisfaction / Subjective Acceptance	x	x	x	x	x	x
Study Lens Distance and Near Visual Acuity	x	x	x	x	x	x
Distance Over Refraction and Visual Acuity	x	x		x	x	

Clinical Study Protocol
Johnson & Johnson Vision Care, Inc.

Visit Information	Visit 1 Screening, Baseline, Treatment 1 Fitting	Visit 2 Treatment 1 Follow-up 1 Optimization	Visit 3 Treatment 1 Follow-up 2	Visit 4 Baseline Treatment 2 Fitting	Visit 5 Treatment 2 Follow-up 1 Optimization	Visit 6 Treatment 2 Follow-up 2
Time Point	Day 0	Day 3±1 from V1	Day 12±2 from V2	Day 7±3 from V3 Fitting Day 0	Day 3±1 from V4	Day 12±2 from V5
Estimated Visit Duration	2.5 hours	1.0 hours	1.5 hours	2.5 hours	1.0 hours	1.5 hours
Lens Fit Assessment	X	X	X	X	X	X
Binocular Over Refraction			X			X
Lens Deposits			X			X
Lens Wettability			X			X
Visual Performance			X			X
Modifications	X	X		X	X	
Post-Fit PRO Questionnaire	X	X		X	X	
Worn Lens Collection		X	X		X	X
Baseline PRO Questionnaire	X					
Study Lens PRO Questionnaire		X	X		X	X
Distance and Near Exit Visual Acuity	X	X	X	X	X	

Clinical Study Protocol
Johnson & Johnson Vision Care, Inc.

Visit Information	Visit 1 Screening, Baseline, Treatment 1 Fitting	Visit 2 Treatment 1 Follow-up 1 Optimization	Visit 3 Treatment 1 Follow-up 2	Visit 4 Baseline Treatment 2 Fitting	Visit 5 Treatment 2 Follow-up 1 Optimization	Visit 6 Treatment 2 Follow-up 2
Time Point	Day 0	Day 3±1 from V1	Day 12±2 from V2	Day 7±3 from V3 Fitting Day 0	Day 3±1 from V4	Day 12±2 from V5
Estimated Visit Duration	2.5 hours	1.0 hours	1.5 hours	2.5 hours	1.0 hours	1.5 hours
Dispensing Criteria	x	x		x	x	
Instructions	x	x	x	x	x	
Schedule Follow-up	x	x	x	x	x	
Final Evaluation						x

Clinical Study Protocol
Johnson & Johnson Vision Care, Inc.

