7.2. Detailed Study Procedures

VISIT 1

Subjects must report to the visit wearing their habitual contact lenses to accurately assess baseline PRO (CLUE and MRD) performance. If the subject is not wearing their lenses they must be rescheduled.

Visit 1: Screening		
Step	Procedure	Details
1.1	Statement of Informed Consent	Each subject must read, understand, and sign the Statement of Informed Consent before being enrolled into the study. The Principal Investigator or his/her designee conducting the informed consent discussion must also sign the consent form. Note: The subject must be provided a signed copy of this document.
1.2	Demographics	Record the subject's age, gender, race and ethnicity.
1.3	Medical History and Concomitant Medications	Questions regarding the subjects' medical history and concomitant medications.
1.4	Habitual Lenses	Questions regarding the subject's habitual lens type and parameters.
1.5	Contact Lens History	Record the subject's correction type (i.e. monovision, multifocal, sphere with readers, etc.).
1.6	Wear time and Comfortable Wear time with Habitual lenses	Record the subjects wear time and comfortable wear time with their habitual contact lenses.
1.7	Eligibility after Screening	All responses to Screening Inclusion Criteria questions must be answered "yes" and all responses to Exclusion Criteria must be answered "no" for the subject to be considered eligible.

Visit 1: Baseline		
Step	Procedure	Details
1.8	Baseline PRO (CLUE and MRD) and CLDEQ-8 Questionnaires	The subject will evaluate the vision characteristics, comfort characteristics, handling characteristics, and visual symptoms of their habitual lenses using the PRO questions.

Clinical Study Protocol
Johnson & Johnson Vision Care, Inc.

1.9	Ocular Symptoms	Subjects will respond to a verbal open-ended symptoms questionnaire.	[REDACTED]
1.10	Entrance Visual Acuity	
Distance and near Snellen visual acuity will be measured for each eye with the subject's habitual contact lenses in place.
 
For near measures use the ETDRS 2000 Series Chart 1 or 2.
 
The acuity will be recorded to the nearest letter OD, OS and OU.
	[REDACTED]
1.11	Lens Removal	Have the subject remove their habitual lenses and store in an approved storage solution.	[REDACTED]
1.12	Keratometry	Keratometry will be performed OD and OS and the steep and flat dioptric power and corresponding meridians recorded.	[REDACTED]

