1.21	Lens Selection	Select the lens pair and power based on the Randomization and fitting guide for each eye. Record the test lens parameters (power and lot number).	Appendix G (Fitting Guide)
1.22	Lens Insertion	
Subjects will insert the lenses themselves. If the lens is uncomfortable, inspect for damage and remove, reinsert or replace as necessary.
 
Damaged lenses will be stored in labeled vial with sterile saline, and clearly differentiated from the other worn lenses that will be shipped back to the Sponsor. Complete the Quality Product Complaint form.
	
1.23	Lens Settling	Allow the study lenses to settle for a minimum of 10 minutes.	
1.24	Determine Visual Satisfaction	Determine if the subject’s vision is acceptable with the lenses. Allow the subject to look down a hallway or out of a window for distance vision assessments, and for them to	

Clinical Study Protocol
Johnson & Johnson Vision Care, Inc.

		read a book, magazine or similar for near vision.	
1.25	Study Lens Distance and Near Visual Acuity	
Measure the distance and near visual acuity OD, OS and OU. Record the results.
 
Note: Use the ETDRS 2000 Series Chart 1 or 2 near card placed at 40 cm to measure the Near visual acuity
	[REDACTED]
1.26	Distance Over-Refraction and Distance Visual Acuity	
Perform a distance over-refraction OD and OS using loose lenses outside of the phoropter under ambient room illumination. The distance over-refraction may also be refined under binocular conditions. Record the results. The results of the distance over-refraction may also be checked for the impact on near vision under monocular and/or binocular conditions.
	
1.27	Lens Fit Assessment	
Evaluate and grade lens centration, primary gaze movement, upgaze movement and tightness (push-up test).
 
 • The subject should not proceed to wear the lenses if any of the following is observed: • presence of limbal exposure (appearance of clear cornea) in any gaze • presence of edge lift • presence of unacceptable movement (excessive or insufficient) in all three movement categories (primary gaze, upgaze, and push-up). 
If either lens is deemed unacceptable, the subject will be discontinued from the study. Remove the lenses, perform a slit-lamp evaluation, and complete the Final Evaluation form.
	[REDACTED]

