3.8	Visual Performance Distance (4M) Intermediate (64 cm) Near (40 cm)	
Visual performance will be recorded OD, OS, and OU for the following:
 
Distance, Bright Illuminance High and Low Contrast ETDRS Charts 4M- HC#1, HC#2, HC#3 and LC#1, LC#2, LC#3
 
Near, Bright Illuminance Reduced Guillon-Poling Charts Intermediate (64 cm) High Contrast and Low Contrast Near (40 cm) High Contrast and Low Contrast
 
Distance, Dim Illuminance (with Distance goggles) High Contrast ETDRS Charts 4M-HC#4, HC#5, HC#6
 
Near, Dim Illuminance (with Near goggles) Reduced Guillon-Poling charts High Contrast Intermediate (64 cm) and Near
	

Clinical Study Protocol
Johnson & Johnson Vision Care, Inc.

		
(40 cm).
 
Note:
 
 • The room illuminance must be between 7.3 and 7.9 EV (394-597 lux). • Distance, HC-1 Chart luminance Acceptable Range 10.5-10.7 EV (181-208 cd/m²). • Guillon-Poling, Near Chart Luminance Acceptable Range 10.8-11.1 EV (223-274 cd/m²). • Do not use the Mesopic filter for Dim luminance (Dim luminance will be simulated by using the goggles) 	
3.9	Binocular Distance Over-refraction and Distance Visual Acuity	
Perform a binocular over-refraction and record the OD and OS results and distance visual acuity.
 
Note: No lens changes are allowed based on the over-refraction.
	Appendix D
3.10	Lens Fit Assessment	
Evaluate and grade lens centration, primary gaze movement, upgaze movement and tightness (push-up test).
 
 • The subject should not proceed to wear the lenses if any of the following is observed: • presence of limbal exposure (appearance of clear cornea) in any gaze • presence of edge lift • presence of unacceptable movement (excessive or insufficient) in all three movement categories (primary gaze, upgaze, and push-up). 
If either lens is deemed unacceptable, the subject will be discontinued from the study. Remove the lenses, perform a slit-lamp evaluation, and complete the Final Evaluation form.
	
3.11	Lens Deposits	Grade and record the amount of front and back surface lens deposits for both eyes.	
3.12	Lens Wettability	Grade the wettability of the lenses.	
3.13	Collection of unworn lenses (if applicable)	Collect unworn lenses returned by the subject.	

Clinical Study Protocol
Johnson & Johnson Vision Care, Inc.

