3.14	Lens Removal	
Have the subject remove the study lenses and store in saline in a labeled glass vial.
 
NOTE: Lenses do not need to be stored in a refrigerator.
	
3.15	Biomicroscopy	
Perform Biomicroscopy OD and OS. Slit Lamp Classification Scales will be used to grade the findings.
 
For the conjunctival redness [REDACTED] 0.5 unit increments will be used in the grading.
 
Corneal Staining Assessment [REDACTED] will be graded in 1.0 increments.
 
If any of these slit lamp findings are Grade 3 or higher, an AE must be recorded. All AEs must be followed to resolution.
 
If the clearance of the fluorescein needs to be expedited, preservative-free rewetting drops may be instilled.
	[REDACTED]
3.16	Distance and Near Exit Visual Acuity	
Distance and near Snellen visual acuity will be measured for each eye with the subject's habitual correction in place.
 
For near measures use the ETDRS 2000 Series Chart 1 or 2.
 
The acuity will be recorded to the nearest letter OD, OS and OU.
	[REDACTED]
3.17	Schedule Follow-up	
The subject will complete a wash-out period and be scheduled to return for their next visit in 7 ± 3 days.
 
NOTE: Subject may wear their habitual spectacles or contact lenses during the washout period.
	

VISIT 4

The subjects may present to Visit 4 wearing their habitual spectacles or contact lenses, if required for their distance vision.

Visit 4: Baseline Treatment 2		
Step	Procedure	Details
4.1	Adverse Events and Concomitant Medications Review	Review the subject's concomitant medications and record any changes from the previous study visit.

Clinical Study Protocol
Johnson & Johnson Vision Care, Inc.

		Record any adverse events or medical history changes from the previous study visit.	
4.2	Subject Reported Ocular Symptoms	Subjects will respond to a verbal open-ended symptoms questionnaire.	[REDACTED]
4.3	Distance and Near Entrance Visual Acuity	
Distance and near Snellen visual acuity will be measured for each eye with the subject's habitual correction in place.
 
For near measures use the ETDRS 2000 Series Chart 1 or 2.
 
The acuity will be recorded to the nearest letter OD, OS and OU.
	[REDACTED]
4.4	Lens Removal (if applicable)	Have the subject remove their habitual lenses and store in an approved storage solution.	

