14.5. Primary Analysis

Visual Performance:

Binocular visual performance at 2-week follow-up visit will be analyzed separately by lighting condition and distance using a Bayesian repeated measurement random-effects model to compare between Test and Control lenses. Each regression model will include baseline values, lens type, lens wearing sequence and lens wearing period as fixed effects and investigational site as random effect. Other subject characteristics such as age, gender will be included as fixed effects when appropriate. Unstructured covariance matrix will be used to model the residual errors among observations within subjects. Non informative prior distributions will be used for the coefficients in the models as well as for the error terms. Independent vague normal $N(0,1000)$ priors will be used for the regression coefficients, inverse gamma $IG(0.001, 0.001)$ for the variance of the random effect site and inverse Wishart for the residual errors. A Markov-Chain Monte Carlo (MCMC) sampling algorithm will be used to carry out the marginal posterior distributions of the parameters. Results will be reported as regression coefficient mean estimates with 95% credible intervals.

The null and alternative hypotheses for non-inferiority of Test lens relative to Control are as follows:

$$H_0: \Delta > 0.05$$
$$H_A: \Delta \leq 0.05$$

where Δ is the posterior mean difference in visual performance between Test and Control (Test minus Control). Non-inferiority will be declared if the upper bound of the credible interval of the posterior mean difference is less than 0.05.

The primary analysis will be conducted on the per-protocol population. A sensitivity analysis will be conducted on the ITT population.

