14.10. Procedure for Reporting Deviations from Statistical Plan

The analysis will be conducted according to that specified in above sections. There are no known reasons for which it is planned to deviate from these analysis methods. If for any reason a change is made, the change will be documented in the study report along with a justification for the change.

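### Does the undefined baseline covariate in Section 14.5 put the nine primary visual-performance models at risk?

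*Combined protocol and SAP*

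**What the plan says.** Section 14.5 fits a separate model for each distance and lighting condition, nine in all, and for each of them states: "Each regression model will include baseline values, lens type, lens wearing sequence and lens wearing period as fixed effects". Site is a random effect and the within-subject covariance is unstructured. The section names no variable, visit, chart or eye for the baseline.

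The endpoint is binocular logMAR acuity at the two-week visit. In Table 3 the row "Visual Performance" is marked only under Visits 3 and 6, which agrees with steps 3.8 and 6.8 of Section 7.2 ("Visual performance will be recorded OD, OS, and OU for the following").

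The acuities available before then are:

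- **Visit 1, before randomisation:** entrance acuity in habitual contact lenses (1.10), best-corrected distance acuity (1.13) and near acuity after ADD refinement (1.17). The visit opens with "Subjects must report to the visit wearing their habitual contact lenses to accurately assess baseline PRO (CLUE and MRD) performance".
- **Visit 4, before the second fitting:** entrance acuity in habitual correction (4.3), under the heading "Visit 4: Baseline Treatment 2". Here "The subjects may present to Visit 4 wearing their habitual spectacles or contact lenses, if required for their distance vision".
- **At fitting, after randomisation:** acuity through the assigned study lens (1.25 and 4.12). Step 1.25 reads "Measure the distance and near visual acuity OD, OS and OU. Record the results".

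**The concern.** Read strictly as the baseline of the outcome, the covariate does not exist. No intermediate, low-contrast or dim-light acuity is taken before Visit 3, so seven of the nine endpoints lack even an approximate counterpart. Only distance and near acuity in bright light at high contrast have one.

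Read loosely, three substitutes are open: a Visit 1 value, period-specific entrance acuity from Visits 1 and 4, or study-lens acuity at fitting. The third is measured through the lens being compared. Adjusting for it would remove part of the lens effect and pull an inferior Test lens towards non-inferiority. If the choice were left until data were in hand, the trial's main conclusion could depend on it. Section 14.10 offers only after-the-fact disclosure: "If for any reason a change is made, the change will be documented in the study report along with a justification for the change".

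**Working it through.** **Inputs.** Margin 0.05 logMAR (Section 2.3). SDs and ICCs from Table 5. 40 completers of 48 enrolled (Section 14.2). Per-protocol set primary, ITT as sensitivity (Section 14.3).

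**Reproducing the plan's figures.** SD of the paired difference = sqrt(s_T² + s_C² − 2·ICC·s_T·s_C). For distance, bright, high contrast: sqrt(0.091² + 0.094² − 2·0.60·0.091·0.094) = sqrt(0.006852) = 0.0828. The smallest n with noncentral-t power of at least 0.90 at one-sided 0.025 is 31, as in Table 5. All nine rows reproduce (31, 29, 31; 34, 38, 36; 36, 40, 40), and power at n = 40 is 0.90 to 0.97. The sample size used a paired t-test with no covariate, so it does not depend on this question.

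**Reading 1: one Visit 1 value per subject.** For subject i in sequence g, write D_i = y_i1 − y_i2 and S_i = y_i1 + y_i2.

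- A term β·x_i that is the same in both periods cancels from D_i. So do the site effect, age and gender.
- The likelihood factors as p(D)·p(S | D). Sequence is in the model, so the mean of S is free in each sequence and S adds nothing about the mean of D.
- The lens effect is half the difference between the two sequence means of D. It is therefore the same with or without x.
- Simulation check 1: 60 crossovers of 40 complete pairs, unstructured covariance and random site (assumed site SD 0.02, covariate correlation 0.5). Largest change in the lens estimate: 2e-15.
- Simulation check 2: 200 data sets with unequal sequence sizes and no site term. Largest change: 1e-15.

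In ITT, subjects with one period contribute S-type information, so the estimate can move. With 40 pairs and 48 − 40 = 8 period-1-only subjects, the shift had SD 0.0011 and maximum 0.0039 in 60 trials. The mean standard error was 0.0122 without the covariate and 0.0121 with it. A typical shift is thus 0.0011/0.0122 = 9% of a standard error, and the largest is 0.0039/0.05 = 8% of the margin.

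**Reading 2: entrance acuity at Visits 1 and 4.** Neither value is measured through a study lens. Spectacles at Visit 4 add noise, but randomisation balances it across sequences. In simulation at a true difference of 0.05 the mean estimate stayed at 0.050, and false non-inferiority was 2.4% (distance, bright, high contrast) and 3.4% (near, dim), against 2.5% nominal. Bias needs unequal carryover into Visit 4: bias = b·(λ_T − λ_C)/2, where b is the covariate slope and λ the carryover from each lens. For a bias of 0.005 (a tenth of the margin) at an assumed b of 0.6, the carryovers would have to differ by 2·0.005/0.6 = 0.017 logMAR after a washout of 7 ± 3 days.

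**Reading 3: study-lens acuity at fitting.** Adjusted difference = 0.05 − b·θ, with θ the lens difference already present at fitting. Distance, bright, high contrast, n = 40, fitting differences assumed to have the same SD as the endpoint differences:

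| b | Estimate, θ = 0.05 | False non-inferiority, θ = 0.05 | False non-inferiority, θ = 0.025 |
|---|---|---|---|
| 0 | 0.050 | 2.5% | 2.5% |
| 0.2 | 0.040 | 9.5% | 5% |
| 0.4 | 0.030 | 28% | 12% |
| 0.6 | 0.020 | 65% | 27% |

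Both b and θ are assumptions; the documents give neither.

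**Is Reading 3 what the plan means?** Section 5.1 lists baseline information among the things to be collected before randomisation. Randomisation is step 1.20, and step 1.25 comes after it. Section 7.2 puts steps 1.8 to 1.19 in a Visit 1 baseline table and steps 1.20 onward in a lens-fitting table. It splits Visit 4 the same way: 4.1 to 4.6 are baseline, 4.7 onward are fitting. Steps 1.25 and 4.12 both fall in fitting tables. Study-lens acuity is also a poor candidate in practice. Up to two lens modifications are allowed at the fitting visit and up to two more at the optimisation visit, so the value may come from a lens not worn at Visit 3 or 6.

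**The case for a change.** The strongest case for acting is that a primary model should be reproducible from its text, and this one is not. Table 3 merges baseline and fitting in its column headings for Visits 1 and 4, so study-lens acuity does sit in a column labelled baseline. Site staff know which lens is worn. The harmful choice errs in the sponsor's favour, and one sentence would close it off. Picking a covariate for an undefined term might not even count as a change under Section 14.10.

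Part of this stands: the term is undefined, no rule fixes the variable before data exist, and a sentence would cost nothing. What does not stand is the step from there to a threatened result. The merged headings are a layout summary; Section 5.1 and the step-by-step tables are specific and point the other way. The larger error rates need a strong correlation. With equal SDs, b = 0.6 means a correlation of 0.6 between lens differences measured from about 10 minutes after insertion and those about two weeks later, and nothing in the documents supports that figure.

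**Conclusion.** The observation is correct and the gap is minor: Section 14.5 calls for a covariate that the schedule does not supply in the form of the endpoint. An analyst following Section 5.1 and the Section 7.2 tables would use a pre-randomisation Visit 1 acuity or omit the term, and the two give the same per-protocol answer (exactly under maximum likelihood, and up to simulation error under the vague priors of Section 14.5). The ITT sensitivity analysis moves by about 0.001 logMAR, 0.004 at most in the trials simulated, against a margin of 0.05. Entrance acuity at Visits 1 and 4 is unbiased unless carryover differs between lenses after the washout. The CLUE models in Section 14.7 are not affected, because CLUE is collected in habitual lenses at Visit 1.

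This conclusion rests on complete pairs in the per-protocol set, on at most about 8 of 48 subjects with one period in ITT, and on baseline meaning what Sections 5.1 and 7.2 make it mean. Naming the variable would tidy the text but change no result, so no change to the plan is called for.

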14.6. Secondary Analysis

All secondary endpoints will be summarized with descriptive statistics at baseline and follow-up visits for each study lens type. Safety variables will be summarized on safety population and efficacy variables on both per-protocol and ITT populations.

14.7. Other Exploratory Analyses

Comfort and Vision CLUE Scores

CLUE comfort and vision CLUE scores will be analyzed separately using the same statistical method described in the primary analysis. Posterior mean differences (δ) in CLUE scores between Test and Control will be calculated with 95% credible intervals. The probability of achieving non-inferiority using a margin of -5 point in the CLUE scale, $Pr(\delta \geq -5 | \text{data})$, will be calculated.

Clinical Study Protocol

Johnson & Johnson Vision Care, Inc.

Further exploratory analysis will be conducted if necessary, at the discretion of the Study Responsible Clinician.

14.8. Interim Analysis

No interim analysis is planned in this study

14.9. Procedure for Handling Missing Data and Drop-Outs

Missing or spurious values will not be imputed. The count of missing values will be included in the summary tables and listings.

Subject dropout is expected to be one of the main reasons of missing data in this clinical trial. Past clinical trials don't provide the evidence that subject dropout is systematic or not-at-random. To evaluate the impact of missing data, sensitivity analysis may be conducted using multiple imputation methods. The SAS/STAT procedures PROC MI and PROC MIANALYZE will be utilized with a parametric regression method used to make at least 20 imputations.

